9.9.1.1 Analysis Populations

The primary analysis population will include all HCPs who have completed at least 1 of the primary effectiveness endpoint questions in the survey. Denominators used to calculate knowledge levels for individual survey questions will reflect the number of respondents who completed the particular survey question including responses of 'I don't know/not sure'.

In the event that the study is conducted in 2 waves, HCP responses from both waves will be combined to comprise the primary analysis population.

9.9.1.2 Statistical Methods

Data analysis will be performed by ICON qualified personnel in accordance with ICON's SOPs for statistical analysis and programming. All analyses will be performed using appropriate statistical software (e.g., SAS[®] Version 9.0 or later). A report summarising the results of the survey will be developed.

The primary criteria is the composite knowledge level for the core question set. The composite will be an opportunity/denominator based weighted percentage of HCPs who have answered each item correctly (if at least 30 HCPs have completed the item).

Other criteria include measures of receipt and reading of the ENJAYMO™ Physician's Guide, knowledge levels for each question regarding the information included in the ENJAYMO™ Physician's Guide (i.e., all questions relating to all domains), assessed as the percentages of HCPs with correct responses to each question, the distribution of HCPs' responses regarding their experience with patients' receptivity to vaccination and the implementation of vaccination (date of vaccination versus treatment start, if the prescriber administered the vaccinations), and the distribution of responses regarding the primary source(s) from which HCPs learned about the information included in the ENJAYMO™ Physician's Guide.

Descriptive data analyses will be conducted for all primary and secondary objectives. Descriptive statistics for continuous data will include N, means, and standard deviations. Results for some continuous variables may include ranges (minimums and maximums) and medians as well. Categorical data will be summarised using frequency counts and percentages. Knowledge levels will be calculated with 95% 2-sided CI. Knowledge levels will also be stratified by items with potential to confound the knowledge level (e.g., country, specialty, reads/uses vs. did not read/does not use the ENJAYMO™ Physician's Guide,

prescribing status). Missing data will be reported, but no replacement or imputation will be performed.

For each primary endpoint, the weighted average percentage of HCPs who answered the core question set correctly will be estimated and assessed against the 80% (\pm 95% CI) target (if the number of HCPs who answered the item is at least 30).

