100	9.6	50.4, 69.6	9.0	61.0, 79.0	7.8	72.2, 87.8	5.9	84.1, 95.9

Note: Calculated using PASS 12 software,* confidence intervals for 1 proportion, simple asymptotic formula.

* Hintze, J. (2014). PASS 12. NCSS, LLC. Kaysville, Utah, USA. www.ncss.com.

Data Analysis:

The primary analysis population will include all HCPs who have completed at least 1 of the primary effectiveness endpoint questions on the survey. The primary criteria is the weighted percentage of HCPs with correct responses to the key question set.

In the event that the study is conducted in 2 waves, HCP responses from both waves will be combined to comprise the primary analysis population.

Other criteria include measures of receipt and reading of the ENJAYMO™ Physician's Guide, knowledge levels for each question regarding the information included in the ENJAYMO™ Physician's Guide (i.e., all questions relating to all domains), assessed as the percentages of HCPs with correct responses to each question, the distribution of HCPs' responses regarding their experience with patients' receptivity to vaccination, and the distribution of responses regarding the primary source(s) from which HCPs learned about the information included in the ENJAYMO™ Physician's Guide.

[figure not shown]
All analyses will be performed using appropriate statistical software (e.g., SAS® Version 9 or later). Data analyses will be descriptive. For continuous variables, counts, means (with standard deviations), medians (with interquartile ranges, minimum, and maximum) will be provided. For categorical variables, frequencies and percentages (with 95% CI) will be provided. Missing data will be reported, but no replacement or imputation will be performed.

Knowledge levels will be calculated with 95% 2-sided CI. Knowledge levels will also be reported by relevant subgroups (e.g., country, prescribers vs. potential, reads/uses vs. did not read/does not use the ENJAYMO™ Physician's Guide).

For each primary endpoint, the weighted average percentage of HCPs who answered all the questions in the core question set correctly will be estimated and assessed against the 80% (\pm 95% CI) target (if the number of HCPs who answered all questions is at least 30).

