9.2.1 Primary

The primary endpoint is knowledge levels of key information included in the ENJAYMO™ Physician's Guide across these 4 domains (assessed by 6 questions):

- Indication for CAD patients only (question 3)
- Important potential risks of serious infections including meningococcal infections (questions 4 and 6)
- Recommendations for vaccination of patients as per local regulations (question 5)
- Recommendations for monitoring and counseling patients to promote real-world safe-use conditions (questions 7 and 8).

The primary endpoint is a composite endpoint based on the percentages of HCPs with correct responses to questions included in the composite. The composite is the weighted average knowledge level across the core question set (6 questions) from the above domains. Success

criteria for the primary endpoint percentage is at least 80% of HCPs have answered the item correctly (if the number of HCPs who answered is at least 30).

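### The 30-respondent condition on the primary 80% criterion is worded three ways, and one wording lets drop-off remove core questions from the six-question composite

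*Protocol*

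**What the plan says.** The protocol states the minimum of 30 in three forms.

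- **Per item.** Section 9.9.1.2 makes the composite a "weighted percentage of HCPs who have answered each item correctly (if at least 30 HCPs have completed the item". Its closing sentence, on the comparison with 80%, repeats the condition as "if the number of HCPs who answered the item is at least 30".
- **On those who answered, object not named.** Section 9.2.1 sets success as "at least 80% of HCPs have answered the item correctly (if the number of HCPs who answered is at least 30". The Synopsis has the same sentence under Variables.
- **On those who answered everything.** The Synopsis, under Data Analysis, compares with 80% "if the number of HCPs who answered all questions is at least 30".

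Section 9.2.1 also fixes the content of the endpoint: "The composite is the weighted average knowledge level across the core question set (6 questions) from the above domains". One of its four domains rests on the last two core questions alone: "Recommendations for monitoring and counseling patients to promote real-world safe-use conditions (questions 7 and 8".

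Three other provisions determine how item counts behave. Section 9.9.1.1 admits "all HCPs who have completed at least 1 of the primary effectiveness endpoint questions in the survey" and uses a separate denominator for each question. Section 9.9.1.2 rules out imputation. The questionnaire (Annex 3) lets respondents move only forward, question by question.

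Sections 9.1.1 and 9.3 provide for a second wave when the first yields fewer than 30 completed surveys, and Section 9.9.1.1 pools the waves. The protocol does not say what happens to the composite if an item is still below 30 after that.

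**The concern.** Taken at its word, the condition in 9.9.1.2 is an inclusion rule: a core question with fewer than 30 completers does not enter the composite. The content of the primary endpoint would then depend on observed completion and would not be fixed beforehand. In a forward-only survey that keeps partial responders, break-off can only hold counts level or lower them from question 3 to question 8. The first questions to fall below 30 would be 8 and then 7. Losing both removes the monitoring and counselling domain, yet the remainder would still be set against 80% as the four-domain endpoint of 9.2.1.

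The other wordings do not lead there. Under the Synopsis (Data Analysis) the same drop-off stops the assessment altogether. Under 9.2.1 the six questions stay in. At stake is whether a shortfall ends in a pass, a fail or no verdict on the study's one success criterion.

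**Working it through.** **1. The plan's own figures.** Section 9.7 gives a precision of 11.1% for 50 HCPs at 80%. The simple asymptotic half-width is 1.96 × √(0.80 × 0.20 / 50) = 11.1 points, which reproduces it. The invitation count also reproduces: 50 / 0.05 = 1,000. At the threshold of 30 the half-width is 1.96 × √(0.16 / 30) = 14.3 points.

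**2. One data set, three readings.** The counts are assumed, because the protocol gives none. Each question is scored as one item, and the point estimate is compared with 80%, because the role of the interval in the target is not stated.

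| Question | 3 | 4 | 5 | 6 | 7 | 8 | Total |
|---|---|---|---|---|---|---|---|
| Completed | 33 | 33 | 32 | 31 | 29 | 28 | 186 |
| Correct | 28 | 29 | 27 | 26 | 19 | 18 | 147 |

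Composite = sum of correct answers / sum of completed answers over the included questions.

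- All six questions (composite of 9.2.1): 147/186 = 79.0%, below 80%.
- Per-item rule of 9.9.1.2, so questions 7 and 8 drop out: (147 − 19 − 18)/(186 − 29 − 28) = 110/129 = 85.3%, above 80%.
- Synopsis (Data Analysis): at most 28 HCPs answered all six, fewer than 30, so no comparison is made.

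**3. When the first two readings disagree.** With near-equal denominators, let a be the mean percentage correct on questions 3–6 and b the mean on 7–8. The six-question composite is (4a + 2b)/6, which is below 80 when b < 240 − 2a.

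- Fail on six, pass on four: a = 82 needs b < 76; a = 85 needs b < 70; a = 90 needs b < 60.
- Pass on six, fail on four: a = 78 needs b ≥ 240 − 156 = 84.

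**4. How often the situation can arise.** Let N be the final number of HCPs answering question 3 and d an assumed constant break-off per question. Question 6 is then answered by a Binomial(N, (1−d)³) number of HCPs, and each of these goes on to answer question 7 with probability 1−d. The chance that question 6 keeps at least 30 while question 7 falls below 30, so that the whole domain is lost, is:

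| N | d = 1% | 2% | 5% | 10% |
|---|---|---|---|---|
| 32 | 6% | 17% | 10% | 0.3% |
| 36 | <0.1% | 1.5% | 27% | 9% |
| 40 | ~0 | ~0 | 9% | 32% |
| 50 | ~0 | ~0 | ~0 | 15% |

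These are conditional on N as the final total; they are not overall chances. If 50 surveys are actually completed, every core question has at least 50 answers and the issue cannot arise.

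**5. Is a final count near 30 credible?** Section 9.7 cites pooled completion proportions of 2.1% and 4.7%, the latter with a 95% interval of 3.0–6.6%. Per 1,000 invited this gives 21, 47 and, at the lower limit of 3.0%, 30 completed surveys. These are completers, so neither 21 nor 47 is itself a problem case. At 47 every item exceeds 30. At 21, having 30 answers early on would need break-off of 1 − 21/30 = 30%. The exposed zone lies between the two, just below 30 completes.

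**The case against.** The strongest reply is that the protocol guards this threshold. In a forward-only survey, fewer than 30 answers at question 7 means fewer than 30 completed surveys, which triggers a second wave that is pooled with the first. Section 9.1.1 adds reminders, wider outreach, more countries and a longer survey period. A shortfall of one or two answers would usually be repaired. This stands, and it limits the problem to a final pooled count that is still short. It does not remove it: there are at most two waves, and the protocol is silent on a remaining shortfall.

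A reader might infer more: that the per-item rule is the plan's settled rule, and that it would tend to turn a fail into a pass because the last questions are the hardest. The documents support neither. Section 9.2.1 and the Synopsis contradict the per-item reading, and under the Synopsis (Data Analysis) the same drop-off gives no verdict, not a pass. Nothing shows that questions 7 and 8 are harder; their multi-part format is only suggestive, and step 3 shows that the shift can go either way.

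It can also be said that the analysis is descriptive, with no prior hypothesis, and that every question is reported separately as a secondary endpoint. The lost domain would therefore remain visible. That is true, but the protocol still sets a success criterion on the composite.

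**Conclusion.** The point holds as a contradiction in the primary decision rule. The 30-HCP condition is attached to the item, to those who answered, and to those who answered all questions, and these are not equivalent. The per-item wording, taken literally, also conflicts with the six-question, four-domain composite of Section 9.2.1.

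The consequence is conditional. It needs a final pooled count below 30 at question 7 or 8 with 30 or more on earlier questions, which is very unlikely at the target of 50. Where it occurs, identical data can give 79.0%, 85.3% or no verdict. Those figures and the probabilities rest on assumed counts and break-off rates; the contradiction does not. It should be corrected because it governs the shortfall case for which a minimum of 30 exists.

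**What to change.** State in Sections 9.2.1 and 9.9.1.2 that the composite always contains all six core questions (3–8), each with its own denominator, and delete the per-item condition from the composite in 9.9.1.2.

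Apply one 30-HCP condition to the whole success assessment. Word it identically in the Synopsis (Variables and Data Analysis), 9.2.1 and the closing sentence of 9.9.1.2. The existing Synopsis wording, "if the number of HCPs who answered all questions is at least 30", would serve. If the condition is not met, report the composite and its interval descriptively, without a success verdict.

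Applying the minimum to the primary analysis population would be weaker. That population counts anyone who answered a single core question, so it would allow a verdict with 30 answers at question 3 and, say, 15 at question 8, and it would still contradict the Synopsis.

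The cost is aligned wording in these places, carried into the SAP before database close. The small downside is that no verdict may be possible if fewer than 30 HCPs answer all six questions.

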9.2.3 Other Endpoints

The survey includes HCP characteristics and other outcomes that may be treated as covariates for data analysis. These questions are described in Table 9-2.

Table 9-2 Other outcomes collected in the survey

Data collected	Variable type	Operation definition/derivation
Years practicing as a physician	Categorical	< 5 years, 5 to <10 years, 10 to <15 years, ≥15 years, prefer not to answer
Number of patients for which the HCP has prescribed ENJAYMO™	Categorical	None, <5 patients, 5-10 patients, >10 patients, prefer not to answer
HCP confirmed distribution of the ENJAYMO™ Patient Guide	Categorical	Yes, no, I don’t know/am not sure
HCP confirmed vaccination status in the patient most recently prescribed ENJAYMO™	Categorical	Yes, no, I don’t know/am not sure
Vaccines HCP checked in the patient most recently prescribed ENJAYMO™	Categorical	Meningococcal conjugate vaccine(s), meningococcal serogroup B vaccine(s), pneumococcal vaccine(s), Other (please specify), I don’t know/am not sure
Vaccines up-to-date in the patient most recently prescribed ENJAYMO™	Categorical	Yes, no, I don’t know/am not sure
HCP administered or prescribed vaccines to the patient most recently prescribed ENJAYMO™	Categorical	Yes, no, I don’t know/am not sure
Reason HCP did not provide vaccines to the patient most recently prescribed ENJAYMO™	Categorical	The patient refused vaccination, the patient received vaccination elsewhere, I don’t know/am not sure
Timing of vaccination relative to starting ENJAYMO™ in the patient most recently prescribed ENJAYMO™	Categorical	At the same time ENJAYMO™ treatment was started, less than two weeks before ENJAYMO™ treatment was started, two weeks before ENJAYMO™ treatment was started, I don’t know/am not sure

HCP counselled the patient most recently prescribed ENJAYMO™ to seek immediate medical attention if they experience symptoms of serious infection	Categorical	Yes, no, I don't know/am not sure
Investigator in ENJAYMO™ clinical trial	Categorical	Yes, no, prefer not to answer
Involvement with CADENCE patient registry	Categorical	Yes, no, prefer not to answer

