9.6 Variables

The survey questionnaire includes the following:

- Screening questions to determine eligibility for survey participation,

- Questions regarding the receipt, reading, and use of the ENJAYMO™ Physician's Guide,
- Questions regarding the dissemination of the ENJAYMO™ Patient Guide,
- Questions to assess knowledge of the core messages included in ENJAYMO™ Physician's Guide,
- Questions to assess HCPs' experience with patients' receptivity to vaccination (asked of HCPs who have prescribed ENJAYMO™ only), and
- Brief questions on HCP characteristics.

The main survey questions are described in [Sections 9.2.1](#) and [9.2.2](#) and Table 9-1 and 9-2.

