[Preamble 1]: These questions are about the risks of serious infections and meningococcal infections associated with ENJAYMO™ (sutimlimab). Please be sure to review all response choices for each question before answering each question. Please note that you will only be able to move forward in the survey as you complete each question.

CORRECT RESPONSES ARE CHECKED ✓

1. Did you receive the “ENJAYMO™ Physician’s Guide” that provides information to minimise the risks of serious infections and meningococcal infections associated with product use?
 - Yes
 - No
 - I don’t know/am not sure

2. Did you read the “ENJAYMO™ Physician’s Guide” that provides information to minimise the risks of serious infections and meningococcal infections associated with product use?
 - Yes
 - No
 - I don’t know/am not sure

3. ENJAYMO™ (sutimlimab) is indicated in adult patients with cold agglutinin disease (CAD) for the treatment of (Check all that apply) **RANDOMIZE ORDER OF THE FIRST 5 RESPONSES**
 - Hemolytic anaemia
 - Jaundice
 - Cardiac arrhythmia
 - Nausea and vomiting
 - Cold agglutinin syndrome
 - I don’t know/am not sure

4. ENJAYMO™ (sutimlimab) should only be prescribed to patients who have received appropriate vaccinations, especially against encapsulated bacteria.
 - True
 - False
 - I don’t know/am not sure

5. Are you familiar with current local guidelines or recommendations in patients with persistent complement deficiencies for meningococcal conjugate vaccine(s), meningococcal serogroup B vaccine(s), and pneumococcal vaccine(s)?

Yes
 No
 I don't know/am not sure

6. According to the ENJAYMO™ (sutimlimab) **Summary of Product Characteristics** and the “**ENJAYMO™ Physician’s Guide**”, which of the following warrant specific caution when using ENJAYMO™ (sutimlimab)? Please select all that apply.

Neisseria meningitides infection
 Hemophilus influenza infection
 Streptococcus pneumoniae infection
 Urinary tract infection
 All of the above
 I don't know/am not sure

7. According to the “**ENJAYMO™ Physician’s Guide**”, which of the following are important activities that are necessary when using ENJAYMO™ (sutimlimab):

		Yes, needs to be monitored	No, does not need to be monitored	I don't know/am not sure
A	Monitor patients for kidney damage			

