B	Monitor patients for signs and symptoms of serious infections			
C	Take caution when prescribing ENJAYMO™ to patients who have chronic infections such as Hepatitis B, Hepatitis C or HIV			
D	Counsel patients about the risks of serious infection including meningitis			
E	Monitor patients for thyroid function			
F	Counsel patients about the risks of abnormal heart function			

8. According to recommendations in the “**ENJAYMO™ Physician’s Guide**,” you should counsel patients to seek immediate medical attention if they experience symptoms associated with risks of serious infections or meningococcal infections associated with ENJAYMO™ (sutimlimab). Please answer “True”, “False” or “I don't know/am not sure” to the following symptoms:

		True	False	I don't know/am not sure
A	Headache with stiff neck or back or confusion			
B	Fever, chills and rash			
C	Loss of appetite			
D	Muscle aches with flu-like symptoms			
E	Swelling in legs, ankles and feet			
F	Polyuria, dry mouth and blurred vision			

9. What is (are) the **primary source(s)** you use to learn about the appropriate indication, precautions for use, and potential risks for ENJAYMO™ (sutimlimab)? Please select all that apply. There are no correct/incorrect answers: **SELECT ALL THAT APPLY ANSWER – NO CORRECT RESPONSE.**

- Summary of Product Characteristics
- ENJAYMO™ Physician's Guide
- Professional Society or Congress
- The European Medicines Agency website
- Via specific discussions with Sanofi MSL
- Clinical practice guidelines; specify: _____
- Other (not listed above); specify: _____

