[ON-LINE SURVEY - PROGRAMMER: RANDOMISE THE ORDER OF THE FIRST 5 RESPONSE OPTIONS]

HCP CHARACTERISTICS

[Preamble 2]: Below are 7 additional questions to help us combine your answers with other answers we have received, and to help us interpret the survey results. **THERE ARE NO CORRECT RESPONSES TO QUESTIONS 10, 11, 19, and 20. DISPLAY QUESTIONS 12-18 ON THE SAME PAGE.**

10. Approximately how many years have you been practicing as a physician?
- <5 years
 - 5 to <10 years
 - 10 to <15 years
 - ≥15 years
 - Prefer not to answer
11. Approximately how many patients have you treated with ENJAYMO™ (sutimlimab)?
- None → **PROCEED TO QUESTION 20**
 - < 5 patients → **PROCEED TO QUESTION 12**
 - 5-10 patients → **PROCEED TO QUESTION 12**
 - >10 patients → **PROCEED TO QUESTION 12**
 - Prefer not to answer → **PROCEED TO QUESTION 20**
12. For the most recent patient you prescribed ENJAYMO™ (sutimlimab), did you provide the patient with a copy of the ENJAYMO™ Patient Guide?
- Yes → **PROCEED TO QUESTION 13**
 - No → **PROCEED TO QUESTION 13**
 - I don't know/am not sure → **PROCEED TO QUESTION 13**
13. For the most recent patient you prescribed ENJAYMO™ (sutimlimab), did you confirm that their vaccination status is up-to-date according to local guidelines or recommendations for patients with persistent complement deficiencies?
- Yes → **PROCEED TO QUESTION 14**
 - No → **PROCEED TO QUESTION 19**
 - I don't know/am not sure → **PROCEED TO QUESTION 19**

14. For the most recent patient you prescribed ENJAYMO™ (sutimlimab), which vaccines did you check the status of? Please select all that apply.
- Meningococcal conjugate vaccine(s)
 - Meningococcal serogroup B vaccine(s)
 - Pneumococcal vaccine(s)
 - Other (not listed above); specify: _____
 - I don't know/am not sure
15. For the most recent patient you prescribed ENJAYMO™ (sutimlimab), was the patient up-to-date on their vaccinations?
- Yes → **PROCEED TO QUESTION 19**
 - No → **PROCEED TO QUESTION 16**
 - I don't know/am not sure → **PROCEED TO QUESTION 19**
16. For the most recent patient you prescribed ENJAYMO™ (sutimlimab), did you administer or prescribe vaccines to the patient?
- Yes → **PROCEED TO QUESTION 18**
 - No → **PROCEED TO QUESTION 17**
 - I don't know/am not sure → **PROCEED TO QUESTION 19**
17. For the most recent patient you prescribed ENJAYMO™ (sutimlimab), what was the reason you did not provide vaccination?
- The patient refused vaccination → **PROCEED TO QUESTION 19**

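### Section 9.9.1.2 stratifies knowledge by specialty, which the survey never collects, and by use of the Guide, for which Annex 3 has no dedicated question

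*Protocol*

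**What the plan says.** Protocol Section 9.9.1.2 commits to reporting knowledge levels "stratified by items with potential to confound the knowledge level (e.g., country, specialty, reads/uses vs. did not read/does not use" the Guide, and then adds prescribing status. The Synopsis (Data Analysis) gives a shorter list of subgroups, "country, prescribers vs. potential, reads/uses vs. did not read/does not use the ENJAYMO™ Physician's Guide", without specialty.

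Section 9.6 describes the content of the questionnaire and lists "Questions regarding the receipt, reading, and use of the ENJAYMO™ Physician's Guide" as one component. Section 9.2.3 introduces Table 9-2 with the statement "The survey includes HCP characteristics and other outcomes that may be treated as covariates for data analysis".

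Annex 3 holds the questionnaire itself. On the Guide, question 1 asks about receipt and question 2 about reading: "Did you read the “ENJAYMO™ Physician’s Guide” that provides information to minimise the risks of serious infections". The block on HCP characteristics opens with question 10, "Approximately how many years have you been practicing as a physician".

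**The concern.** A stratified analysis needs a variable to stratify on. If the survey does not collect that variable and nothing else supplies it, the analysis is lost at data collection. The statistical analysis plan can define strata from the available data, but it cannot create an item the questionnaire lacks. Section 9.1.1 says a second wave would use the same survey, so the gap would carry over.

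The study has no comparator, so comparing HCPs who read or use the Guide with those who do not is one of the main ways to relate knowledge to the Guide. Specialty could plausibly confound that comparison. Eligibility does not restrict it: screening question S1 asks only whether the practice includes patients with cold agglutinin disease, so respondents may come from several specialties that cannot be told apart. The ENCePP checklist (Annex 4, items 7.1, 8.1 and 10.5) answers yes on confounding, effect modification and analytic control of confounding. The stratification sentence in Section 9.9.1.2 is the main text behind those answers.

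**Working it through.** No figure is at stake, so the check is a comparison of each named stratifier with the items collected.

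What the survey collects (Annex 3):

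- Entry: country and language.
- S1 to S3: cold agglutinin disease patients in the practice, permission to share responses, employment.
- Questions 1 and 2: receipt and reading of the Guide.
- Questions 3 to 8: knowledge items.
- Question 9: primary sources of learning, several answers allowed.
- Questions 10 and 11: years in practice, number of patients treated with the product.
- Questions 12 to 19: Patient Guide, vaccination, counselling.
- Questions 20 and 21: trial investigator, CADENCE involvement.

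Table 9-1 defines variables for the knowledge items, receipt, reading and source. Table 9-2 covers questions 10 to 21. Neither adds a variable that Annex 3 lacks.

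The four stratifiers in Section 9.9.1.2 against that list:

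| Stratifier | Item | Can it be run? |
|---|---|---|
| Country | Survey entry | Yes |
| Prescribing status | Question 11 | Yes |
| Reads/uses the Guide | Question 2 for reading; none for use | On reading only |
| Specialty | None | No |

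**Other sources for specialty.** Section 9.1.1 describes recruitment lists but does not say they hold specialty. Checklist item 9.4 marks linkage between data sources as not applicable. No source outside the questionnaire is described.

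**Question 9 as a stand-in for use.** It asks about the primary sources "you use to learn about the appropriate indication, precautions for use, and potential risks", with the Guide as one option. That concerns where knowledge came from, not whether the Guide is used in practice. An HCP who applies the Guide but learned mainly from the Summary of Product Characteristics could leave it unticked. One who learned from the Guide but no longer consults it could tick it. It can misclassify use in both directions.

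Count: two of four stratifiers are fully supported, one is supported for its reading half, and one is not supported.

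**The case against.** The strongest reply is that the inconsistency is narrow. The planned factor combines reading and use, reading is collected in question 2 and defined in Table 9-1, and question 9 adds something on use. This stands: a reader might infer that neither analysis can be run, but only the specialty one cannot.

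It can also be said that strata may come from outside the survey. Section 9.11 plans to stratify by time since distribution of the Guide, which no survey item collects, and invitation codes could in principle tie respondents to contact lists. The documents do not say that those lists hold specialty, so this leaves a possible rescue but no planned one. For the same reason the loss should not be called irrecoverable. Section 9.8 bars contact only to clarify or revise knowledge answers, and the Annex 3 introduction has respondents agree to contact about the survey.

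A reader might further infer that leaving trial-investigator status and CADENCE involvement out of the named strata is an error. It is not. The list in Section 9.9.1.2 is given as examples, both items are collected (questions 20 and 21), and Section 9.2.3 already allows them as covariates. Nor is reads/uses the only internal contrast: receipt (question 1), source of learning (question 9) and time since distribution also bear on the Guide.

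Finally, the analyses are descriptive, with no a priori hypothesis (Section 8.2), and the 80% target does not depend on these strata. That limits the consequence but does not supply the missing variable.

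**Conclusion.** The point holds in two parts. Specialty is a named stratifier with no data item and no described source, so that stratification cannot be run as the protocol stands. Section 9.6 misstates the questionnaire by saying it asks about use of the Guide, so the reads/uses stratum reduces to reading, with question 9 as a weak proxy for use.

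This is an internal inconsistency affecting a secondary, descriptive analysis. The composite knowledge estimate and its comparison with the 80% target can be computed as planned. A claim that the primary result is compromised would go beyond the documents. They also give no basis for putting a number on the confounding left unexamined, so none is offered.

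The conclusion assumes that Annex 3 is the questionnaire to be fielded and that no unstated source, such as the contact lists, supplies specialty.

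**What to change.** If the survey has not launched, add two closed questions to Annex 3: the HCP's specialty, next to question 10, and whether the HCP uses the Guide in practice (yes, no, don't know), next to question 2. Add matching rows to Tables 9-1 and 9-2. Numbering them 2a and 10a would keep the references to questions 3 to 8 in Section 9.2.1 and Table 9-1 intact. The cost is a slightly longer survey and translation into German, Italian and Dutch.

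If it has launched, which is possible because Section 6 plans the start of data collection for Q2 2024 and this version is dated 05 June 2024, delete specialty from Section 9.9.1.2 and use from the Synopsis, Section 9.6 and Section 9.9.1.2. Define the stratum as read versus not read from question 2, and state where its don't-know answers go. This costs only a text amendment, but gives up both planned analyses. Adding the questions in a second wave alone would leave first-wave respondents without them.

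Stratifying by questions 20 and 21 as well is an optional addition that needs no new data.
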